9.4. Vital Signs

Descriptive summaries of observed values and change from baseline will be calculated for systolic blood pressure, diastolic blood pressure, heart rate, and body temperature by visit and treatment within cohort. Shift from baseline categories for weight (change <-5%, change between -5% and 5%, and change >5%) will be provided by visit and treatment for Cohort 2 only, as no post-baseline weight was recorded for Cohort 1.

9.5. 12-Lead Electrocardiogram

Frequencies and percentages of investigator interpretation of ECG results (normal, abnormal clinically significant, and abnormal not clinically significant) will be presented by visit and treatment within cohort.

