8.1.2 Clinical Studies

This will be the first study of topical ARQ-151 cream in the human population.

However, oral roflumilast (DALIRESP®, DAXAS®) has been approved globally for the treatment of COPD and has been evaluated in nine Phase III/IV randomized double-blind clinical trials ([Wedzicha 2016](#)). Overall, the safety of oral roflumilast has been well established in its targeted population of mostly middle- and upper-aged individuals who currently smoke cigarettes or have smoked them extensively in the past. Adverse events (AEs) reported with roflumilast tablets have been consistent with those expected for oral PDE-4 inhibitors. In a pooled analysis of safety data from 6-month and 1-year clinical trials (N=8630), the most common AEs were diarrhea, weight loss and nausea. Other AEs reported more frequently with roflumilast treatment than with placebo were back pain, influenza, insomnia and decreased appetite ([Michalski 2012, Wedzicha 2016](#)).

In addition to the self-reported cases of weight loss in the 6-month and 1-year trials, clinically significant weight loss was also reported in two prospective studies that evaluated weight ([Michalski 2012](#)).

Psychiatric-related AEs were also greater in patients treated with roflumilast tablets (5.9%) compared to those treated with placebo (3.3%). The most common psychiatric-related AEs were insomnia, depression and anxiety. A small number of cases of completed suicide and suicide ideation have been reported in patients taking oral roflumilast in clinical trials and also during post-marketing experience ([Michalski 2012](#)).

The only contraindication to oral roflumilast, other than hypersensitivity to components of the product, is in patients with moderate to severe liver impairment (Child-Pugh B or C), where systemic levels of roflumilast may become highly elevated.

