8.12.3 Vital Signs and Weight

Blood pressure, heart rate, temperature, and weight will be measured at every visit for both Cohorts.

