9.3 Safety Evaluation

The following analyses will be performed; however, no formal inferential statistics will be performed on safety assessments.

Descriptive statistics will be calculated for quantitative safety data and frequency counts will be compiled for classification of qualitative safety data.

Adverse Events:

The assessment of safety will be based mainly on the frequency and percent of subjects who reported treatment-emergent AEs.

Adverse events will be coded using the Medical Dictionary for Drug Regulatory Activities (MedDRA) Version 18.1 or higher. Treatment emergent adverse events (i.e. events with onset dates on or after the start of study drug or with missing onset dates) will be summarized by presenting for each treatment group, the number and percentage of subjects having any AE, having an AE in an individual body system, and having an AE in an individual preferred term. Any other information collected (e.g. severity or relatedness to study medication) will be listed as appropriate.

Application Site Reaction

The numeric application site reaction scores will be summarized individually by using number and percentage of subjects by visit.

Medical History and Physical Examinations:

Medical history for all subjects will be presented in a by-subject listing.

Physical examination findings for all subjects will be presented in a by-subject listing. Changes in physical examinations will be described in the text of the final report.

Clinical Laboratory Results, Electrocardiograms and Vital Signs Measurements:12

All clinical laboratory results, 12-lead ECGs and vital signs measurements and their change from baseline (pre-dose), will be summarized along with time point of collection.

A shift table describing out-of-normal range shifts will be provided for clinical laboratory results.

Prior and Concomitant Medications:

Prior and concomitant medication information for all randomized subjects will be presented in a by-subject listing. Summary tables will be presented by World Health Organization-Anatomical Therapeutic Chemical Classification System (WHO-ATC) therapeutic category and product.

Quick Inventory of Depressive Symptomatology-Self-Report (QIDS-SR):

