14.3.6 Other Safety Data Summary Tables		
Table 14.3.6.1.1	Safety	Summary of Quantitative Dermal Response Reaction by Study Visit, Treatment, and Cohort
Table 14.3.6.1.2	Safety	Summary of Qualitative Dermal Response Reaction by Study Visit, Treatment, and Cohort
Table 14.3.6.1.3	Safety	Summary of Application Site Reaction Other Effects by Study Visit, Treatment, and Cohort
Table 14.3.6.2.1	Safety	Summary of Vital Signs by Study Visit, Treatment, and Cohort
Table 14.3.6.2.2	Safety	Shift from Baseline in Weight by Study Visit, Treatment, and Cohort
Table 14.3.6.3	Safety	Summary of 12-Lead Electrocardiogram Interpretation by Study Visit, Treatment, and Cohort
Table 14.3.6.4.1	Safety	Summary of Quick Inventory of Depressive Symptomatology-Self-Report (QIDS-SR) Total Score by Study Visit, Treatment, and Cohort
Table 14.3.6.4.2	Safety	Summary of Quick Inventory of Depressive Symptomatology-Self-Report (QIDS-SR) Total Score Severity Levels by Study Visit, Treatment, and Cohort
Table 14.3.6.4.3	Safety	Shift from Baseline in Quick Inventory of Depressive Symptomatology-Self-Report (QIDS-SR) Total Score Severity Levels by Study Visit, Treatment, and Cohort
Table 14.3.6.5	Safety	Summary of Concomitant Medications by ATC Class Level 4, PT, Treatment, and Cohort

AD-ST-33.04 Effective date: 30-Jun-2017

Statistical Analysis Plan,
Sponsor Arcutis, Inc.
Protocol Number ARQ-151-101
PCN Number ARCU7063

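### Cohort 2 body weight after baseline is summarised only as a ±5% shift, so a small mean loss could go unseen in the planned weight table

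*SAP*

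**What the plan says.** **The risk.** Protocol 8.1.2 reports that in pooled 6-month and 1-year trials of oral roflumilast "the most common AEs were diarrhea, weight loss and nausea". It adds that "clinically significant weight loss was also reported in two prospective studies that evaluated weight". It gives no size or SD for that loss.

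**The data.** Protocol 8.12.3 states: "Blood pressure, heart rate, temperature, and weight will be measured at every visit for both Cohorts". The Cohort 2 flow chart shows weight at Screening, Baseline and Weeks 1, 2, 3 and 4. For Cohort 1 the flow chart shows weight only at Screening and Day 1, and SAP 9.4 says none was recorded after baseline. The every-visit statement and the Cohort 1 schedule should be reconciled, but this point concerns Cohort 2.

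**The planned summaries.** SAP 9.4 states: "Descriptive summaries of observed values and change from baseline will be calculated for systolic blood pressure, diastolic blood pressure, heart rate, and body temperature". Weight is not in that list. For weight in Cohort 2 the section says: "Shift from baseline categories for weight (change <-5%, change between -5% and 5%, and change >5%) will be provided by visit and treatment". The matching output is Table 14.3.6.2.2, "Shift from Baseline in Weight by Study Visit, Treatment, and Cohort". SAP 7.3 summarises weight numerically, but only as a baseline characteristic.

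**The general rule.** Protocol 9.3 and SAP 9 both commit to descriptive statistics for quantitative safety measurements and frequency counts for qualitative ones.

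**The concern.** Weight is a numeric measurement tied to a risk the protocol names, yet by the SAP text its only post-baseline summary is a count in three wide bands. Other safety measures get both forms. Laboratory values have change from baseline and shifts (SAP 9.3), dermal response scores are summarised numerically and by category (9.2), and QIDS-SR has a total score and severity levels (9.6). SAP 10 even drops the categorical summary of cream used, on the ground that a weight is continuous. Body weight gets the opposite treatment, and no reason is given.

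A cut at -5% over 28 days discards most of the information about a small shift in the mean. An empty band could be read as reassurance, and it would not show whether the two strengths differ. This is the first human study of the cream, so the four weekly post-baseline weights by arm are worth reporting in full.

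**Working it through.** **1. Inputs from the documents.** 84 subjects randomised 1:1:1 gives 84/3 = 28 per arm. Treatment lasts 28 days. The bands are cut at -5% and +5%.

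**2. The plan's own figure.** The documents state no figure for weight. The only related figure is the sample size, which fixes the arm size. With difference 23, SD 25, two-sided α = 0.025 and 80% power, n per arm = 2 × (2.241 + 0.842)² × (25/23)² = 22.5, so 23 by the normal formula. The exact t calculation at 24 per arm gives power 0.805. The stated 24 is reproduced.

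**3. Assumptions not in the documents.** The 28-day percent change in weight is normal with mean -m on active and 0 on vehicle. The SD s is common to both arms, with s from 1 to 3 points. One visit is considered.

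**4. Formulas.**
- Chance that a subject falls below -5%: p = Φ((-5 + m)/s).
- Chance that the band is empty on an active arm: (1 - p)^28.
- Yardsticks only, since no safety test is planned: power of a two-sided 5% Fisher test on that band, and of a two-sample t test on mean percent change.

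**5. Example, m = 1 and s = 1.5.** p = Φ(-2.67) = 0.0038. Expected count = 28 × 0.0038 = 0.11. Chance of an empty band = (1 - 0.0038)^28 = 0.90. The standard error of the difference in means is 1.5 × √(2/28) = 0.40, so a 1-point loss is 1/0.40 = 2.5 standard errors (3.7 at SD 1, 1.9 at SD 2).

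**6. Range at 28 per arm.**

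| Mean loss | SD | Band empty on active | At least one on vehicle | Fisher power | t-test power |
|---|---|---|---|---|---|
| 1% | 1.0 | 99.9% | 0.0% | 0.0% | 96% |
| 1% | 1.5 | 89.8% | 1.2% | 0.0% | 69% |
| 1% | 2.0 | 52.5% | 16.0% | 0.0% | 45% |
| 1% | 2.5 | 20.6% | 47.5% | 0.2% | 31% |
| 1% | 3.0 | 6.9% | 74.6% | 1.1% | 23% |
| 2% | 1.0 | 96.3% | 0.0% | 0.0% | 100% |
| 2% | 1.5 | 52.5% | 1.2% | 0.0% | 99.8% |
| 2% | 2.0 | 14.4% | 16.0% | 0.8% | 96% |
| 2% | 2.5 | 3.3% | 47.5% | 5.4% | 84% |
| 2% | 3.0 | 0.8% | 74.6% | 10.0% | 69% |
| 3% | 1.0 | 52.5% | 0.0% | 0.0% | 100% |
| 3% | 1.5 | 6.9% | 1.2% | 3.7% | 100% |
| 3% | 2.0 | 0.8% | 16.0% | 24.3% | 100% |
| 3% | 2.5 | 0.1% | 47.5% | 38.6% | 99% |
| 3% | 3.0 | 0.0% | 74.6% | 40.8% | 96% |

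**7. Reading.** An empty band is likely for a 1% loss at SD up to about 1.5, and for a 2% loss at SD near 1. Elsewhere the band often fills. At the wider SDs it also fills on vehicle, so a filled band does not by itself point to the drug. For losses up to 2% the bands seldom separate the arms (10% at most). Means carry more information in every row. With 24 per arm, the 1% loss at SD 1.5 gives an empty band in 91% of trials (1 - 0.088) and t-test power of 62%, so allowing for dropout changes little.

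**The case against.** **Other routes exist.** SAP 6.1.8 and SAP 9 put all collected data in listings, and Listing 16.2.9.2 covers vital signs. Weight loss judged to be an adverse event enters the TEAE tables by treatment, which is largely how the protocol describes the oral risk. This stands, so the shift table cannot be called the only weight output. But a 1% shift need not be reported as an event, and a listing does not compare arms.

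**Unseen shell.** Table 14.3.6.2.1, "Summary of Vital Signs by Study Visit, Treatment, and Cohort", may include weight, because weight shares a flow-chart row and an SAP section with the vital signs. The shells were removed, so this is open. The SAP text names the summarised variables and weight is not among them.

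**No clear breach of the protocol.** A reader might infer that the SAP breaks the promise in Protocol 9.3 that "vital signs measurements and their change from baseline (pre-dose), will be summarized along with time point of collection". The documents do not support that. Protocol 8.12.1 lists vital signs as blood pressure, heart rate and temperature, and 8.12.3 names weight alongside them in its title. The general rule on quantitative safety data points towards a numeric summary, but it is only a general statement.

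**Assumed effect.** The oral data come from longer trials of tablets. This trial applies cream for 28 days to at most 5% of body surface. Nothing in the documents predicts a loss of 1% to 2%, and this stands too. The calculation shows what the table could reveal, not what is expected.

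**A threshold is legitimate.** A per-subject 5% cut is a reasonable screen for marked loss, and safety is descriptive only, so test power is no more than a yardstick. That is a reason to keep the shift table. It does not justify leaving out the mean.

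**Conclusion.** The point holds in a limited form. By the SAP text, the three-band shift is the only planned post-baseline summary of Cohort 2 weight, and a small mean loss could go unseen in it. With 28 per arm and an assumed SD of 1 to 2 points, a 1% mean loss leaves the band below -5% empty in about 52% to 99.9% of trials.

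A reader might go further and infer that a real weight loss would almost certainly not show in the safety tables. The documents do not support that. They give neither an SD nor an effect size, and at SD 2 or more, or with a 2% to 3% loss, a filled band becomes likely over much of the assumed range. Weak separation of the arms is the more durable finding: Fisher power is at most 10% for losses up to 2%, rising to about 41% for a 3% loss at SD 3. This is a worthwhile improvement to safety reporting and does not affect the efficacy conclusions.

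**What to change.** In SAP 9.4 and Table 14.3.6.2.1, add Cohort 2 body weight to the continuous summaries: observed value, change and percent change from baseline, by visit and treatment, with n, mean, SD, median, minimum and maximum. Keep the ±5% shift table as a supplement. If the shell of Table 14.3.6.2.1 already includes weight, only the text of 9.4 needs to say so.

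The cost is one line of SAP text and one more parameter in an existing table. No new measurement, visit or inferential test is needed.

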8.12.4 ECG Monitoring

Single 12-lead ECGs will be performed at Screening for both Cohorts and at Baseline and Week 4 for Cohort 2.

ECGs will be performed on subjects in the supine position. All ECG tracings and readouts will be reviewed by the Study Physician or his/her designee.

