2.2. Study Endpoints

2.2.1. Safety Endpoints

The safety endpoints of this study include the following:

- Treatment emergent adverse events (TEAEs)
- Application site assessments
- Medical history and physical examinations
- Changes in clinical laboratory results
- Changes in 12-lead electrocardiograms (ECGs)
- Changes in vital signs

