8.2. Secondary Efficacy Analysis

The secondary efficacy endpoints for Cohort 2 include the following:

AD-ST-33.04 Effective date: 30-Jun-2017

1. Difference in mean percent change from baseline at weeks 1, 2, and 3 in TPSS x TPA between each dose concentration level of ARQ-151 cream and vehicle control.
2. Difference in mean percent change from baseline at weeks 1, 2, 3, and 4 in TPSS between each dose concentration level of ARQ-151 cream and vehicle control.
3. Difference in mean percent change from baseline at weeks 1, 2, 3, and 4 in TPA between each dose concentration level of ARQ-151 cream and vehicle control.

Each of the secondary efficacy endpoints will be analyzed using MMRM methods similar to the primary endpoint; however, no adjustments for multiplicity will occur, and all analyses will be conducted at the $\alpha = 0.05$ level.

Additionally, descriptive statistics for absolute and percent change from baseline to each week (ie, Weeks 1, 2, 3, and 4) will be presented by treatment group.

9. Safety and Tolerability Analysis

Safety will be evaluated from reported AEs, application site reaction assessments, physical examinations, and changes in clinical laboratory values, vital signs, and 12-lead ECGs.

Descriptive statistics will be calculated for quantitative safety data and frequency counts will be compiled for classification of qualitative safety data. No formal inferential statistics will be performed on safety assessments. Individual subject listings will be prepared for all safety data.

All safety analyses will be performed on the Safety Population for each cohort. All safety data will be presented in the listings.

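### Change in 12-lead ECG is a listed safety endpoint, but the SAP tabulates only the investigator's interpretation visit by visit, so no summary shows within-subject ECG change

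*SAP*

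**What the plan says.** Three statements commit the trial to analysing change in the ECG:

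- SAP section 2.2.1 includes "Changes in 12-lead electrocardiograms (ECGs" in its list of safety endpoints.
- The introduction to SAP section 9 says safety will be judged in part from "changes in clinical laboratory values, vital signs, and 12-lead ECGs".
- Protocol section 9.3 states: "All clinical laboratory results, 12-lead ECGs and vital signs measurements and their change from baseline (pre-dose), will be summarized".

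The planned analysis is narrower. SAP section 9.5 provides "Frequencies and percentages of investigator interpretation of ECG results" in three categories (normal, and abnormal with or without clinical significance), by visit and treatment within cohort. SAP Table 7 lists one ECG table, 14.3.6.3, titled "Summary of 12-Lead Electrocardiogram Interpretation by Study Visit, Treatment, and Cohort". The only other ECG output is the by-subject Listing 16.2.9.3.

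On timing, protocol section 8.12.4 says: "Single 12-lead ECGs will be performed at Screening for both Cohorts and at Baseline and Week 4 for Cohort 2".

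**The concern.** The endpoint is worded as change, but the planned output describes each visit separately. A by-visit table of normal and abnormal readings gives the totals at Baseline and at Week 4 without linking a subject's two readings. New abnormalities and resolved ones can cancel, so stable totals may hide movement in both directions.

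Protocol section 8.1.2 describes this as the first study of the topical cream in humans, and safety is among the primary objectives. Safety results are descriptive only, with no formal tests, so the safety tables carry the evidence. A listed endpoint without a matching summary is a gap in that evidence, and SAP section 10, which records departures from the protocol, does not mention it.

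**Working it through.** The plan states no figure to reproduce here. The check is a comparison of the texts, followed by a short calculation of what by-visit counts can and cannot show.

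**Comparison with the other safety measures**

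| Measure | Worded as change in SAP 2.2.1? | Planned summary of change |
|---|---|---|
| Clinical laboratory | Yes | Change from baseline and shift tables (SAP 9.3) |
| Vital signs | Yes | Change from baseline; shift categories for weight in Cohort 2 (SAP 9.4) |
| 12-lead ECG | Yes | None (SAP 9.5) |
| QIDS-SR severity level | Not a safety endpoint there; change is listed in SAP 2.2.4 | Shift from baseline (SAP 9.6, Table 14.3.6.4.3) |

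Of the three safety endpoints that SAP 2.2.1 words as change, ECG is the only one with no summary of change. The QIDS-SR row shows that the SAP already uses a shift table for an ordered categorical measure, which is the form that ECG interpretation takes.

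**Declared departures**

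SAP section 10 records two: tube weight will not be categorized, and the QIDS-SR severity labels are changed. ECG is not among them.

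**Availability of the data**

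Cohort 2 has an ECG at Screening, Baseline and Week 4 (protocol 8.12.4). SAP 6.1.1 defines baseline as the last observation before first dose. Each Cohort 2 subject with a Week 4 ECG therefore has a pair of readings. Cohort 1 has a Screening ECG only, so no change can be derived there.

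**What by-visit counts leave open**

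Take an arm of n subjects, all with both readings, and combine the two abnormal categories. Let b be the number abnormal at Baseline, w the number abnormal at Week 4, and x the number newly abnormal.

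- Subjects abnormal at both visits number w − x, which must lie between 0 and b. Hence x is at least w − b and at most w.
- Newly abnormal subjects must come from the n − b who were normal at Baseline.
- So x lies between max(0, w − b) and min(w, n − b).

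With 84 subjects randomized 1:1:1, n = 84/3 = 28. The counts below are assumptions, since the documents give no ECG abnormality rate.

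| b | w | Lowest x | Highest x |
|---|---|---|---|
| 0 | w | w | w |
| 3 | 3 | max(0, 0) = 0 | min(3, 25) = 3 |
| 4 | 4 | max(0, 0) = 0 | min(4, 24) = 4 |
| 4 | 6 | max(0, 2) = 2 | min(6, 24) = 6 |
| 6 | 4 | max(0, −2) = 0 | min(4, 22) = 4 |

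In the second row, 3/28 = 10.7%, so the same table is compatible with 0% or 10.7% of the arm becoming abnormal on treatment. The first row shows that the ambiguity disappears when no subject is abnormal at Baseline.

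**The case against.** The strongest reply is that the information is not lost. Listing 16.2.9.3 shows every subject's ECG, sorted by cohort, treatment and subject. With about 28 subjects per arm, a reader could count the changes by hand. That is true, but a listing is not the summary that protocol 9.3 promises, and laboratory and QIDS-SR data are also listed yet still get shift tables.

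An ECG change of concern could also be reported as an adverse event and tabulated there, and protocol 9.3 rests the safety assessment chiefly on treatment-emergent events. This is partial cover, because it depends on the investigator choosing to record an event.

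Protocol 9.3 promises a shift table for laboratory results only. That is correct: the protocol's commitment for ECG is to change from baseline, and a shift table is one way of meeting it. It is the natural one for a three-category reading.

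ECG is not the only categorical measure summarized by visit alone; qualitative urinalysis and dermal response have similar tables. However, application site assessments are not worded as change in SAP 2.2.1, and laboratory data as a class do receive change and shift summaries.

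Finally, inclusion criterion 8 requires good health judged partly on the ECG, so baseline abnormalities may be few, and with none the planned table would suffice. This limits the practical size of the problem. It does not remove it, because the criterion leaves the matter to the investigator's judgment and does not require a normal tracing.

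**Conclusion.** The concern holds. SAP 2.2.1, the introduction to SAP section 9 and protocol 9.3 all call for change in the ECG. SAP 9.5 and Table 14.3.6.3 do not supply it, and SAP section 10 does not declare the departure.

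It is a minor point. It is confined to Cohort 2, touches no efficacy result, alpha or power, and matters numerically only if some subjects have abnormal ECGs at Baseline. The range of 0 to 3 of 28 rests on assumed counts and on every subject having both readings.

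Two things cannot be seen. The table shells were removed from the public SAP, so the layout of Table 14.3.6.3 is judged from its title and the text of SAP 9.5; the planned shift tables elsewhere are labelled as shifts in their titles. The documents also do not say whether numeric ECG intervals are recorded. The shift in interpretation does not depend on them.

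**What to change.** Add to SAP 9.5 and Table 7 a Cohort 2 table that cross-classifies ECG interpretation at Baseline against Week 4, by treatment arm, in the Safety Population. It should keep the three existing categories and include a row or column for missing readings. State that Cohort 1 is excluded because it has no ECG after dosing; SAP 9.4 already makes the same restriction for weight.

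If numeric ECG intervals are on the CRF, add descriptive statistics for their change from baseline. If they are not, record in SAP section 10 that this part of protocol 9.3 will not be done, with the reason.

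The cost is one extra table from data already collected, in a format the SAP already uses for QIDS-SR.
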